# List of Common Abbreviations in Protocol:

- MCC: Multiple chronic conditions
- **CT**: Community Team
- UPMC ISD: University of Pittsburgh Medical Center Insurance Services Division
- HTE: Heterogeneity of treatment effects
- **ODP**: Optimal Discharge Planning

## **Research Synopsis**

**Study Population:** Medicaid or dual-eligible (Medicare-Medicaid) adults aged 21 years and older with multiple chronic conditions (MCC), including at least one physical health condition and at least one additional physical or behavioral health condition, beneficiaries/members of our partnering health care payer, and identified as having high and/or rising health care needs and at risk for unplanned health care use.

**Study Design:** A comparative effectiveness study using an individual-level, randomized design along with a pragmatic, mixed-methods approach to compare three strategies (e.g., in-person and telephonic supported care, technology-supported care, and optimal discharge planning care) all of which include evidence-based components of integrated care. Quantitative (e.g., self-report, claims, process) and qualitative (e.g., interviews) data will be collected across multiple timepoints during the study period.

Sample Size: We expect to enroll 1,400 individuals.

Study Duration: The contract period begins January 1, 2018 and concludes November 30, 2024.

## **Background and Significance**

Chronic disease is widely recognized as the U.S. public health challenge of the 21st century. Defined as "conditions that last a year or more and require ongoing medical attention and/or limit activities of daily living," these diseases comprise a wide range of physical illnesses, such as diabetes, arthritis, asthma, heart disease, chronic obstructive pulmonary disease, and hypertension, as well as mental health and substance use disorders. Among the Medicaid population, 80% of high-need beneficiaries have three or more chronic conditions, and 60% have five or more chronic conditions, including a high incidence of behavioral health issues. Three in five of the 9 million individuals eligible for both Medicare and Medicaid (e.g. dualeligible) services have multiple chronic physical conditions, 20% have more than one mental/cognitive condition, and almost two in five have comorbid physical/behavioral health conditions.

Although numerous randomized controlled trials have shown that practice-based integrated chronic care models assisting patients and their caregivers in managing their health and health care can improve outcomes for various chronic conditions, including comorbid medical and behavioral health issues, implementation of these models has been limited due to the significant upfront financial and infrastructure investments that are typically required. Related interventions, such as transitional care, self-management education, and coordinated care, have also been proven effective in improving outcomes for adults with multiple chronic conditions (MCC), but there is still considerable uncertainty about how best to implement these practices to achieve widespread and significant impact. The fact that different approaches may be required in order to optimally support specific patient subgroups adds a further layer of complexity. For example, there is very little information available about how to effectively support Medicaid and dual-eligible enrollees, who are often sicker, report lower health and functional status, and are more likely to be disabled than their

Medicare-only counterparts. Targeting intensive care management services to these highneed patients is an increasingly well-recognized best practice.

Despite increased understanding of how to promote optimal care for individuals with MCC, widespread improvements in health outcomes have yet to be realized, especially for high-risk, high-need subgroups. There have been no head-to-head trials comparing the effectiveness of system-level interventions in supporting the delivery of evidence-based integrated care for adults with MCC in general or the Medicaid and dual-eligible populations to date. The proposed study will assess innovative approaches of integrated care that can be leveraged to address this gap.

To this end, we propose to compare the effectiveness of the two primary system-level features that drive these programs, namely personalized service design and innovative use of technology in delivering four evidence-based, patient-centered components of established integrated chronic care models: (1) interdisciplinary care team management; (2) development and monitoring of individual care plans; (3) patient education and chronic disease self-management/self-care support; and (4) supporting member linkages with medical/behavioral health and social services. The hybrid nature of the proposed interventions is both unique and compelling. No single, system-level intervention has yet to combine all four components of integrated care that have been proven effective in improving outcomes for patients with MCC.

#### Objectives

The goal of this collaborative study is to provide much needed information for adults living with MCC and other key stakeholders working to support the health of these adults through health care system improvements. The three care strategies, High-Touch (in-person and telephonic supported), High-Tech (technology-supported) and Optimal Discharge Planning (ODP) will be implemented and evaluated to determine their potential to serve as best practice for effectively managing chronic conditions.

To ensure our study's focus was patient-centered, the study team worked closely with the Patient Partner Co-Investigator and patient, provider, and system-level stakeholders to develop all aspects of this study protocol, including the early development efforts of in-person and technology-supported care approaches, the research questions, the study outcomes, the evaluation procedures, and the dissemination strategies included in this protocol.

#### Aims

This study aims to compare the effectiveness of the approaches on patient-centered outcomes and determine which care strategy works best for whom and under what circumstances. By observing comparisons on key outcomes with ODP, our findings will enable patients and health care systems to understand the relative effectiveness of the care strategies vis-à-vis current practice and provide much-needed information for patients with MCC as well as health systems striving to support them more effectively and efficiently.

**Primary Aim 1**: Compare the effectiveness of High-Touch, High-Tech, and ODP on primary outcomes including hospital readmission, health status, and patient activation, and on several

secondary outcomes including functional status, quality of life, care satisfaction, emergent care use, engagement in primary, specialty, and mental health care, and gaps in care.

*Hypothesis 1a:* High-Touch will result in lower readmission rates at 12 months compared to High-Tech & ODP.

*Hypothesis 1b:* High-Touch will result in higher health status at 12 months compared to High-Tech & ODP.

*Hypothesis 1c:* High-Tech will result in higher patient activation at 12 months compared to High-Touch & ODP.

**Primary Aim 2**: Examine the differential effects of the interventions for patient subgroups, based on age, race, illness complexity, and comorbid behavioral health conditions to evaluate heterogeneity of treatment effects (HTE) and determine for whom and under what circumstances the interventions are most effective.

Hypothesis 2a: For all primary outcomes, High-Touch will have greater positive impact than High-Tech & ODP for older participants (60 years or more) and for participants with comorbid behavioral health conditions.

**Primary Aim 3**: Examine perceived barriers and facilitators to efficient and effective implementation of High-Touch and High-Tech interventions for delivering evidence-based integrated care.

## **Interventions Compared**

High-Touch. This approach leverages a personalized service design that includes payeremployed registered nurses and social workers to provide intensive, in-person/telephonic support and resources for eligible participants in their homes and/or communities for a minimum of four months following initial engagement. The health plan-based CT will focus on addressing the full range of health determinants that can impact an individual's health and health care and support information sharing with patients and providers through intervention that do not require access to mobile devices or the Internet.

*High-Tech.* By leveraging telehealth and remote monitoring technology to support selfdirected care management in real time, this approach uses less in-person resources. CT will focus on addressing the full range of health determinants that can impact an individual's health and health care through innovative approaches including virtual visits and access to mobile communications/applications for managing individual health and health care. 

**Optimal Discharge Planning (ODP).** Prior to the use of High-Touch and High-Tech interventions within our payer environment, all members with MCC who were hospitalized and at risk for rehospitalization were supported through the UPMC Health Plan's optimal discharge planning program, considered to be ODP for this study's purposes. After initial engagement via a phone call to the member, a Care Manager from the CT will have an in-home or telephonic visit with each individual to provide evidence-based support, including: detailed disease management and medication education; confirmation of and connection to family/caregiver support and resources; scheduling an ambulatory follow-up appointment; and a hand-off to a health plan-based telephonic care manager, as needed.

## Study Design/Methodology

We have chosen an individual-level randomized design along with a pragmatic, mixed-methods approach to compare three integrated care approaches, High-Touch (in-person/telephonic supported), High-Tech (technology-supported) and ODP for Medicaid or dual-eligible adult members with MCC who reside in in Western, Central, or Eastern Pennsylvania (PA) and are at high risk for high utilization, including rehospitalization.

Quantitative data will be collected from several sources. Self-report data will be gathered at baseline and three additional timepoints (3-, 6-, 12-months) using REDCap Cloud, a secure data collection platform. Claims/administrative data will be collected from UPMC Insurance Services Division (UPMC ISD) to inform several outcomes and covariates. Claims data will be extracted at six months and 12 months to characterize participant service use through each participant's enrollment period, allowing for one full year of service-use observation.

Qualitative telephonic interviews will be conducted with a sample of participants and CT staff to examine perceived barriers and facilitators to efficient and effective implementation of the High-Touch and High-Tech approaches for delivering evidence-based integrated care at three timepoints (Participants: baseline, 3-, and 12-months; CT Staff: baseline, mid- and end-implementation period).

## **Randomization Procedure**

The study will use web-based randomization to one of the three care strategies for those individuals who consent to participate in the study. The consent process may take place faceto-face with an eligible individual, or over the phone, providing that the individual consenting has received a paper or electronic copy of the consent form and enrollment materials to review. Once a member of the CT staff determines the individual's eligibility, they will enter in key identification information, independently or with support of the research team, and the system will then generate a Study ID (numeric identification number). A research team member will verify eligibility and the accuracy of the information entered with the CT staff and enrollee, and then the REDCap Cloud system will provide an assignment to an intervention arm. Randomization will be stratified by gender, type of insurance (Medicaid or Medicare-Medicaid), and technology/digital literacy, which will be assessed at time of enrollment and before randomization, to ensure that intervention arms are balanced with respect to these important variables. Within each stratum, random block sizes of 5 and 10 will be used to maximize balance between intervention groups while minimizing the ability to unmask investigators to the next treatment assignment, triggering an automated alert to CT staff regarding which intervention (care strategy) to implement for each participant and documented accordingly in HealthPlaNET, UPMC ISD's integrated health management software program. If a participant is unwilling to be randomized, they will be excluded from the study.

#### Measures

#### **Process Measures**

Participant and payer care team staff perceptions/experience will be assessed via telephonic qualitative interviews with a sample of participants and CT staff to examine perceived barriers

and facilitators to efficient and effective implementation of High-Touch and High-Tech and to identify strategies for intervention improvement/tailoring and dissemination.

#### **Primary Outcome Measures**

Patient activation will be assessed using the Patient Activation Measure (PAM), a 13-item scale that gauges individual knowledge, skills, and confidence essential to managing one's own health. In consideration of "straight-lined" answers in the PAM measure, (i.e., all 13 questions answered with "strongly disagree"), we plan to include all participant responses and conduct a sensitivity analysis. This is recommended by our study investigative team, including our Patient Partner Co-investigator.

Health status will be measured using the Health Survey (SF-36), a 36-item scale measuring functional health and well-being within eight domains, including physical functioning, physical ability to complete tasks, bodily pain, general health, vitality, social functioning, emotional ability to complete tasks, and mental health.

Subsequent 90-day rehospitalization will be measured using an all-cause readmission rate existing in UPMC ISD inpatient claims for physical and behavioral health service use within 90 days of the last hospital discharge prior to study enrollment. All-cause readmission does not include observation visits.

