## **Secondary Outcome Measures**

Subsequent rehospitalization will be measured using an all-cause readmission rate existing in UPMC ISD inpatient claims for physical and behavioral health service use within 30 days and again at 12 months, following the index inpatient admission. Inpatient and ED visits that were adjudicated and reclassified as Observation visits will be separately explored at 12 months.

Functional status will be measured using the PROMIS Physical Functional Form – Short For 6b which is a brief self-report tool that assesses functional impairment in everyday tasks, household chores, and walking using a 5 point Likert scale.

Quality of life will be measured using the Quality of Life Enjoyment and Satisfaction Questionnaire (Q-LES-Q-18), which is an 18-item, self-administered questionnaire monitoring enjoyment in several domains (physical health, subjective feelings, leisure time activities, social relationships).

Care satisfaction will be measured using the Patient Assessment of Chronic Illness Care (PACIC), a 20-item survey designed to provide an assessment of important aspects of care for chronic illness patients, including specific actions or qualities of care that patients report experiencing in the service delivery system and their satisfaction level.

Emergent care use will be measured using existing behavioral and physical health claims data from the UPMC ISD data warehouse determining participant frequency of emergent service use over 12 months.

Engagement in primary, specialty, mental health care will be measured using existing behavioral and physical health claims data from the UPMC ISD data warehouse determining participant frequency of non-acute visits for participants over 12 months.

Gaps in care will be assessed using Healthcare Effectiveness Data and Information Set (HEDIS) quality metrics that will be compiled using existing behavioral and physical health claims data from the UPMC ISD data warehouse. Gaps in care will be assessed for six of the most common chronic diseases present among our target population, including: asthma, chronic obstructive pulmonary disease, congestive heart failure, coronary artery disease, diabetes, and depression.

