# **Statistical Analysis Plan**

#### Sample Size and Power Calculations

We will evaluate, based on a 20% attrition rate, a total of 1,120 participants at 12-month postenrollment data collection time point, which will be the main time point for the comparison of primary outcomes. We will use a randomization ratio of 2:2:1 (High-Touch; High-Tech; ODP, respectively) and, as such, estimate final sample sizes of n=448 for each active care strategy and n=224 for the ODP strategy. All calculations for the power estimates were done in PASS version 13. For the primary test for the trial, the power calculation is based on the comparison of the two primary care strategies (High-Touch and High-Tech) for the main outcome of hospital readmissions between the strategies, using a two-sample test of proportions; specifically we have 80% power to detect a difference between a readmission rate of 20% in the High-Touch care strategy versus 28% in the High-Tech care strategy. Additionally, for the overall differences between the three care strategies the given sample sizes yield 95% power; based on a chi-squared test.

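### The primary readmission outcome is a 90-day measure in the outcome list but a 12-month measure in Hypothesis 1a and the time-point statements, and the 20% vs 28% behind the 80% power has no stated window

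*Combined protocol and SAP*

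**What the plan says.** All references are to the combined protocol and SAP.

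- **Primary Outcome Measures** defines the primary readmission outcome as an all-cause claims rate "within 90 days of the last hospital discharge prior to study enrollment".
- **Secondary Outcome Measures** lists further readmission outcomes "within 30 days and again at 12 months, following the index inpatient admission".
- **Aims, Hypothesis 1a** reads "High-Touch will result in lower readmission rates at 12 months compared to High-Tech & ODP". Hypothesis 2a extends to every primary outcome: "For all primary outcomes, High-Touch will have greater positive impact than High-Tech & ODP", for older participants and those with behavioral comorbidity.
- **Sample Size and Power Calculations** evaluates "a total of 1,120 participants at 12-month postenrollment data collection time point", "which will be the main time point for the comparison of primary outcomes". It continues: "For the primary test for the trial, the power calculation is based on the comparison of the two primary care strategies", with readmission as the main outcome and "80% power to detect a difference between a readmission rate of 20% in the High-Touch care strategy versus 28% in the High-Tech care strategy". No window accompanies those rates. The age-specific readmission rates later in the same section (22%, 40% and 42% in older participants; 18%, 16% and 28% in younger) have none either.
- **Quantitative Analysis** directs all the described models at the 12-month outcome, again without excepting readmission.

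**The concern.** The outcome headings point to 90 days. The hypothesis and the time-point statements point to 12 months. Followed literally, Hypothesis 1a tests an outcome that the plan labels secondary, while the numbered hypotheses contain no main-effect statement worded for the 90-day outcome.

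This matters because readmission carries the trial's primary test. The two windows can give different answers: one may reach significance and the other not. An analyst could then defend either as the planned result, by citing the headings or by citing the hypothesis. Hypothesis 2a inherits the ambiguity, because what counts as a primary outcome is itself in doubt for readmission. A reader also cannot tell which endpoint the 80% power belongs to.

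**Working it through.** **1. The statements side by side**

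| Section | Window | Counted from | Status |
|---|---|---|---|
| Primary Outcome Measures | 90 days | last discharge before enrolment | primary |
| Secondary Outcome Measures | 30 days; 12 months | index admission, not defined there | secondary |
| Hypothesis 1a | 12 months | not stated | under Primary Aim 1 |
| Sample Size and Power Calculations | 12 months after enrolment, for primary outcomes generally | enrolment | main time point |
| Sample Size and Power Calculations, 20% vs 28% | not stated | not stated | primary test |
| Quantitative Analysis | 12 months, all described models | not stated | main focus |

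**2. The plan's own power figure**

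Inputs from Sample Size and Power Calculations: 1,400 enrolled, 20% attrition, 2:2:1 allocation, two-sample test of proportions. Two-sided 0.05 is an assumption here; the plan states that level only for the Aim 2 interaction tests.

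- n per active arm: 1,400 × 0.8 × 2/5 = 448. Without attrition: 1,400 × 2/5 = 560.
- Power = Φ[(|p1 − p2| − 1.96 × SE0) / SE1].
- SE0 = √(2 × 0.24 × 0.76 / 448) = 0.02854.
- SE1 = √((0.20 × 0.80 + 0.28 × 0.72) / 448) = 0.02841.
- (0.08 − 1.96 × 0.02854) / 0.02841 = 0.847, so power is 80.2%. At 560 per arm it is 88.1%.

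The stated 80% reproduces. The calculation uses only the rates and n, so it cannot show which window was meant.

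**3. Illustration of why the window matters**

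The documents give no hazard shape and no duration of effect. Assume a constant hazard and a constant effect from discharge. The implied hazard ratio is ln 0.80 / ln 0.72 = 0.68.

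- *20%/28% are 12-month rates, tested at 90 days.* 1 − 0.80^(90/365) = 5.35% and 1 − 0.72^(90/365) = 7.78%. Power is 31% at 448 per arm and 37% at 560.
- *The same, with an event-free and untreated gap before randomisation.* The inclusion criteria allow a stay up to 30 days earlier. Assume a 30-day gap, so 60 of 335 at-risk days fall inside the 90-day window: 1 − 0.80^(60/335) = 3.92% and 1 − 0.72^(60/335) = 5.71%. Power is 24% at 448 per arm. A 15-day gap gives 28%.
- *20%/28% are 90-day rates, tested at 12 months.* 1 − 0.80^(365/90) = 59.5% and 1 − 0.72^(365/90) = 73.6%. Power is 99.4% at 448 per arm.

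An effect that fades reverses both directions. Suppose there is no gap and the effect stops at day 182:

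- If 20%/28% are 12-month rates, the hazard ratio needed is 0.36, the 90-day rates are 2.8% vs 7.8%, and power is 91%.
- If they are 90-day rates, the 12-month rates are 67.3% vs 73.6%, and power is 54%.

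These figures depend wholly on the assumed hazard and effect duration. They are not bounds.

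**The case against.** The best defence has four parts.

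*The headings already set a hierarchy.* One window is under the primary heading and the other under the secondary, and Aim 1 names hospital readmission as a primary outcome. This stands in part: a reader might infer that the plan gives no ordering at all, and that would be too strong. What is missing is agreement between those labels and the hypothesis and time-point statements.

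*The phrase in Hypothesis 1a may only mean that the 90-day outcome is taken from the 12-month claims extraction.* No section says so. A window ending 90 days after a pre-enrolment discharge closes long before 12 months, and the secondary list has a separate 12-month readmission outcome that matches the hypothesis wording.

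*The sample size settles the window.* A reader might infer from 448, which is net of 12-month attrition, that 20% and 28% are 12-month rates. The same n serves SF-36 and PAM, so it may simply be one n for all three outcomes. The sources cited for the rates may give a window, but they cannot be seen here.

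*The starting points may not really differ.* The index admission can naturally be read as the qualifying stay in the inclusion criteria, so the two clocks may be the admission and discharge of one stay. That is plausible, and it leaves a definition to write down rather than a separate fault.

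**Conclusion.** The inconsistency is in the current text and must be fixed. It affects the outcome on which the trial's primary test is powered, and the plan as written lets either window be presented as the main readmission result.

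A reader might go further and conclude that the 80% is wrong, or that the trial has only about 31% power. The documents support neither. The arithmetic is sound for the stated rates, with two-sided 0.05 assumed. Power for the other window cannot be derived, because hazard shape, effect duration, time from discharge to randomisation and the n available for a 90-day claims outcome are not given. The illustrative values on either side of 80% show only that the choice of window can matter a great deal. Even the direction of the change is unknown. The contradiction stands without them.

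**What to change.** 1. Name one primary readmission window and one starting point, chosen on the trial's question and not on which preserves power, and record the reason. Make Aims, Primary and Secondary Outcome Measures, Sample Size and Power Calculations, and Quantitative Analysis agree, with the other window secondary.
   - If 90 days: reword Hypothesis 1a and except readmission from the 12-month statements in the two analysis sections.
   - If 12 months: swap the two windows between the primary and secondary lists and define the index event, for example as the qualifying stay in the inclusion criteria.
2. State the window and starting point for 20% vs 28% and for the age-specific readmission rates.
3. State power for the chosen endpoint with the n that applies to it, even if it is below 80%. A 90-day claims outcome need not lose the 20% assumed at 12 months.
4. Record the choice before readmission is tabulated by arm. The documents do not show whether that has already happened. If it has, disclose it and report both windows side by side.

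The cost is wording in up to five sections and restated power. No new data appear to be needed, since claims extractions at 6 and 12 months are planned. There are two downsides. The stated power may fall, and because enrolment goals were expected to be met by Spring 2022, a shortfall after that could only be reported. Relabelling the window is also a change of primary outcome and must be documented as one.

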# Inclusion/Exclusion Criteria

## **Inclusion Criteria**

Individuals who are (1) Medicaid or dual-eligible; (2) age 21 years and older; (3) insured through physical and/or behavioral health payers within the UPMC ISD; (4) identified as members high risk for high utilization including rehospitalization and have had an inpatient hospital stay within the last 30 days; (5) who have at least one physical health condition (e.g. cardiovascular disease, hypertension, COPD, diabetes) and at least one additional physical or behavioral health condition (e.g. depression, serious mental illness, substance abuse disorder); and (6) who reside in Pennsylvania.

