#### **Informed Consent Process**

Informed consent can be obtained either telephonically or obtained during the first in-home visit using a web-based platform, at the participant's home or a preferred location within the community. For telephonic consents, the care manager will provide the participant with a copy of the consent form and study FAQs to review prior to enrollment. CT staff, who have completed the University of Pittsburgh Human Research Protection Office (HRPO) human subjects research training through the Collaborative Institutional Training Institute (CITI), will assist the participant in navigating the web-based consent process, with support provided by the research team. The web-based consent process will provide subjects with a clear explanation of the objectives, procedures, risks and benefits of the study, a frequently asked questions page and their rights as study participants. Research Team members will be available via the telephone to answer all questions related to the informed consent process and the study prior to the member consenting to participation. Consent will be obtained only from the participant. Consent will also be required for participation in the qualitative interviews.

Participants will retain their right to have their questions answered by the Principal Investigator or a member of the Research Team via telephone or an appointment for an inhome visit. The Research Team believes that informed consent is an ongoing process in any study and so will continue to educate participants about the nature of the research and will address any questions that arise throughout the course of the study. These efforts will comply fully with the Health Insurance Portability and Accountability Act (HIPAA) and the informed consent guidelines of the University of Pittsburgh's HRPO.

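### The readmission windows start before randomisation, so 0 to 30 of the 90 primary days, and up to all of the 30-day window, can pass before any arm can act

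*Combined protocol and SAP*

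**What the plan says.** Under Primary Outcome Measures, the 90-day outcome counts all-cause readmissions "within 90 days of the last hospital discharge prior to study enrollment". Under Secondary Outcome Measures, the other two rates are taken "within 30 days and again at 12 months, following the index inpatient admission". The second anchor is an admission, not a discharge, and the protocol does not define which admission is the index.

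Inclusion criterion (4) requires that members "have had an inpatient hospital stay within the last 30 days". The Randomization Procedure describes "web-based randomization to one of the three care strategies for those individuals who consent to participate in the study", after staff have checked eligibility. The Informed Consent Process adds that "Informed consent can be obtained either telephonically or obtained during the first in-home visit using a web-based platform".

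The Statistical Analysis Plan bases the main power calculation on "a readmission rate of 20% in the High-Touch care strategy versus 28% in the High-Tech care strategy" and does not name the window to which these rates apply. Hypothesis 1a under Aims reads "High-Touch will result in lower readmission rates at 12 months compared to High-Tech & ODP".

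No section starts a readmission clock at randomisation, says how a stay between the anchor and randomisation is handled, or gives an expected delay from discharge to randomisation.

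**The concern.** A randomised comparison can show an effect only from the moment of allocation. Here each readmission window opens earlier, by an amount that differs from person to person. A member randomised on the day of discharge has 90 days at risk for the primary outcome. One randomised 30 days after discharge has 60. For the 30-day outcome, counted from admission, that second member's result is already settled when the arm is assigned.

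At stake are the precision of the comparison that sets the sample size and the meaning of the 30-day secondary outcome. There is also a gap in the rules for the 30-day and 12-month outcomes. If the index admission is not the member's last stay before enrolment, a second stay before randomisation could be counted as an outcome event.

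**Working it through.** **Inputs from the documents.** Primary window 90 days from last discharge; secondary windows 30 days and 12 months from the index admission; delay from stay to enrolment at most 30 days; rates 20% v 28%; 448 evaluable per active arm (1,400 × 0.8 = 1,120, split 2:2:1).

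**Assumptions, not in the documents.** Two-sided 5% test for readmission (the plan states this level only for the interaction tests); 20% and 28% are rates over a full 90 days after randomisation; constant hazard; no event can count before randomisation; delay from discharge to randomisation uniform over the ranges shown.

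**Step 1: reproduce the planned power.** With a pooled variance under the null, power = Φ[(d − 1.96·SE0)/SE1].
- d = 0.28 − 0.20 = 0.08
- SE0 = √(2 × 0.24 × 0.76/448) = 0.02854
- SE1 = √((0.20 × 0.80 + 0.28 × 0.72)/448) = 0.02841
- (0.08 − 0.05593)/0.02841 = 0.847, so power = 80.2%

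This matches the stated 80%. The formula requires 447 per arm against 448 planned, so there is no slack.

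**Step 2: share of each window lost before allocation.** Share = days from anchor to randomisation ÷ window length.
- 90-day window from discharge: 0/90 to 30/90, that is 0 to 33%; mean 15/90 = 17% if the delay is uniform over 0 to 30 days.
- 30-day window, if counted from discharge: 0 to 100%. The mean is 12%, 23%, 33% or 50% for delays uniform over 0–7, 0–14, 0–20 or 0–30 days.
- 30-day window as written, from admission: length of stay is added. With a 0–30 day delay and an assumed stay of 3, 5 or 7 days, the mean loss is 59%, 65% or 71%, and 10%, 17% or 23% of participants are randomised after the window has closed.

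**Step 3: effect on the primary comparison.** With delay L, the rate observed is 1 − (1 − p)^((90 − L)/90), averaged over L. For L = 30 in everyone: 1 − 0.80^(2/3) = 13.8% and 1 − 0.72^(2/3) = 19.7%.

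| Delay (days) | High-Touch | High-Tech | Risk ratio | Power |
|---|---|---|---|---|
| 0 | 20.0% | 28.0% | 0.714 | 80.2% |
| Uniform 0–7 | 19.3% | 27.1% | 0.713 | 78.8% |
| Uniform 0–14 | 18.6% | 26.1% | 0.712 | 77.3% |
| Uniform 0–20 | 18.0% | 25.3% | 0.711 | 75.9% |
| Uniform 0–30 | 16.9% | 23.9% | 0.709 | 73.4% |
| All at day 30 | 13.8% | 19.7% | 0.703 | 65.0% |

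The odds ratio moves from 0.643 with no delay to 0.649 with the uniform 0–30 delay. The relative effect is almost unchanged; the loss comes from having fewer events.

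**Step 4: the 12-month window.** Take 20% and 28% as 365-day rates, counted from admission, with a 5-day stay and a uniform 0–30 delay. The rates become 19.0% and 26.7% and power is 78.2%, a loss of about 2 points.

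**The case against.** A discharge anchor is a coherent definition of readmission and matches how a payer reports it. The delay precedes allocation, so it should be balanced across arms by randomisation. The power section names no window: if the planners meant rates under the outcome as defined, among enrolled members, the 80% already allows for the delay and nothing is lost. Thirty days is a ceiling, and quick enrolment would make the loss small. If the hazard falls after discharge, moving the anchor would regain less power than the table shows. All of this stands, and it is why the power figures are given only as a conditional range. It does not remove the unequal time at risk, the two different anchors, or the 30-day results fixed before allocation.

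A reader might infer three stronger things that the documents do not support.

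- That the primary outcome is filled with events no arm could influence, pulling the treatment effect towards zero. The anchor is the last discharge before enrolment, so a readmission completed before enrolment becomes the new anchor. The lost days are therefore largely event-free and the risk ratio hardly moves. A power of 63.1% for a 15-day delay follows only if pre-randomisation events count at a common hazard, which this definition largely excludes.
- That about half or more of the 30-day window is lost. Counted from discharge, half is the mean only under a uniform 0–30 day delay; the admission anchor adds an assumed length of stay. The documents support only the range of 0 to 100%.
- That the primary window is at fault for covering less than an intervention given "for a minimum of four months following initial engagement". That concerns window length, not where the clock starts, and 90 days from randomisation would also fall short of it.

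**Conclusion.** The point holds as a matter of where the clock starts. As written, 0 to 30 days of the 90-day primary window pass before allocation, leaving 60 to 90 days at risk depending on the participant. For the 30-day outcome anything from none to all of the window may be gone, and a participant randomised on day 30 after discharge has none left. For the 30-day and 12-month outcomes, an undefined index also leaves open whether a stay before randomisation can count as an event.

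For the primary outcome the consequence is fewer events and lower power, not bias between arms. On the stated assumptions, power is 78.8% to 73.4% for delays uniform over ranges from 0–7 to 0–30 days, with 65.0% as the extreme. Those figures depend on reading 20% v 28% as full 90-day post-randomisation rates, on constant hazard and on an assumed delay; the plan gives none of these. On a 12-month window the loss is about 2 points. This is a cheap and worthwhile improvement to the endpoint definitions. It does not invalidate the comparison.

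**What to change.** In Primary and Secondary Outcome Measures, start the 30-day, 90-day and 12-month windows at the date of randomisation and count only inpatient admissions that begin after that date. Define the index stay. Optionally, include days from index discharge to randomisation as a baseline covariate in the readmission models. Keep the discharge-anchored rates as descriptive or sensitivity results. In the power section, state the window to which 20% and 28% refer.

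Little or no new data collection should be needed: the randomisation system assigns the arm, and the claims extraction under Study Design/Methodology already follows each participant's enrolment period for a year. There are two costs. The main rate will no longer match the usual discharge-anchored payer metric, which remains available as a supporting result. The definition of a primary endpoint also changes, possibly late, since Data Safety Monitoring places the end of enrolment around spring 2022. The change and its reason must therefore be documented before analysis. If the team prefers not to alter the primary definition, a prespecified randomisation-anchored sensitivity analysis is the minimum, with a note on the limits of the 30-day outcome for late enrollees.
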